5.2 Study setting

This trial will be conducted at the UOHI in the Minto Prevention and Rehabilitation Centre. Specifically, all intake sessions and appointments with participants will be on the Cardiac Rehabilitation Track on the 2nd floor of the UOHI.

5.3 Study population

A total of 32 participants will be included in this study. The study population will be drawn from patients currently enrolled in on-site CR at the UOHI. The sample size calculation is provided in Section 5.6.1. Eligibility criteria are outlined below.

5.3.1 Inclusion and exclusion criteria

Inclusion criteria include:

1. Patient is attending on-site (2 x weekly for 8 weeks) CR at the Minto Prevention and Rehabilitation Centre at the UOHI;
2. Patient is ≥ 18 years;
3. Patient has confirmed diagnosis of coronary artery disease (CAD);
4. Patient understands English or French;
5. Patient is willing and able to provide informed consent.

Exclusion criteria include:

1. Patient is unwilling to wear activity monitors;
2. Patient is already using a commercial activity monitor with sedentary prompts (e.g., Jump Up, Garmin);
3. Patient is unable to attend follow-up visits;
4. Patient is not participating in a CR program at the UOHI;
5. Patient has cognitive impairment (unable to comprehend or participate in the intervention);
6. Patient has a history of postural hypotension;
7. Patient is unable, in the opinion of the Medical Director, to participate in the study.

5.4 Data collection procedures

If a patient expresses interest in participating in research to a health care professional within their circle of care, this will be acknowledged as permission to contact the prospective participant, in order to provide them with study information and determine interest and eligibility. The PI and/or RC and/or study staff may also screen incoming cardiac rehabilitation patients using vOACIS for eligibility in the study. The PI and/or RC and/or study staff will only contact patients who have given permission to be contacted by research to provide them with information about the study and determine if they are interested in participating. Interested individuals will be contacted by the PI and/or RC and/or study staff who will prescreen patients for eligibility and arrange a visit to confirm eligibility and obtain written, informed consent.

Each participant will be asked to complete the following study-related visits: 1) baseline (1 week prior to first CR class), 2) exercise test prior to the first class of CR, 3) 8 weeks of a UOHI CR on-site program, and 4) an 8-week follow-up with post measures. The duration of participation will be 9 weeks. Each component of the study is described in more detail below.

5.4.1 Baseline assessment

Participants will be asked to meet with the research staff 1-week prior to their first CR session. Prior to data collection, written informed consent will be obtained. The research staff will then measure aortic stiffness, blood pressure and resting heart rate using a Mobil-O-Graph device. Participants will be provided with a brief study questionnaire to assess self-efficacy to reduce sedentary behaviour and increase light and moderate PA and HRQoL (SF-36). Participants will be provided with a parking pass for this visit. During the baseline phase, participants will also self-report demographics (e.g., age, sex,

income), exercise (using the modified Godin Leisure-Time Exercise Questionnaire [15]), as well as symptoms of anxiety and depression (Hospital Anxiety and Depression Scale [16]) as part of the CR intake questionnaire which is the usual standard of care. In addition, the study staff will extract several cardiovascular risk factor measurements obtained by CR staff at the participant's Intake Session, including: measured height (cm) and weight (kg) to compute BMI (kg/m^2), waist circumference (cm), total cholesterol, high density lipoprotein (HDL), low density lipoprotein (HDL), triglycerides, and fasting HbA1c. Participants will then be provided with an *activPAL3™* activity monitor, to be worn for seven days on the right thigh under clothing (see product description of the *activPAL3™* device). The *activPAL3™* is worn directly on the skin using a hypoallergenic, hair-friendly adhesive sticker. Participants will also be provided with Hypafix tape to use if they feel more support is needed to secure the device. Participants will also complete a daily log (FITS log) over this period of time to assist with the verification of the data collected while the monitor was worn and for validation of self-reported sedentary time. The research assistant will demonstrate how to properly wear the monitors and answer any questions and the participants will be provided with written instructions (see SIT-CR Baseline Questionnaire).

One week following the baseline measures, participants will be asked to meet approximately 30 minutes before their first session begins to complete the sub-maximal exercise test (Modified Bruce Ramp Treadmill Test) to estimate maximal aerobic power (VO_2max) [17].

5.4.2 Intervention

Following the baseline phase and the sub-maximal exercise test, participants will be randomized in a 1:1 ratio to: 1) usual care (C), 2) usual care + sedentary prompts from the VTAP monitor (I) using a computer-generated, stratified by sex, random sequence. Treatment assignments will be generated and placed in sealed, numbered envelopes to ensure concealment until baseline data is collected.

Both groups will complete a combination of supervised and home-based exercise sessions over an 8-week period (as per standard CR programming). Supervised exercise sessions will take place at the Minto Prevention and Rehabilitation Centre at the UOHI.

Intervention Group participants will also be provided with a VTAP monitor to wear directly on the skin of the front of their right thigh during waking hours for weeks 1 through 7. The monitor will provide participants with real-time feedback on their sedentary behaviour. The VTAP is the world's first commercially available device for free-living sedentary behaviour modification. The VTAP alerts wearers to the fact they have been sitting for a period of time and ought to move. The alerts are delivered by way of gentle vibrotactile feedback (buzzing). The monitors will be programmed to provide feedback once the wearer has been sedentary for 30 consecutive minutes. The monitors will also be able to log the duration and intensity of the primary movements including: sedentary, upright and ambulatory activities of the intervention participants. Due to the battery life of the monitors, each week participants will be provided with a newly charged VTAP and sticker applications at the first CR session of the week. See the product information sheet for the *activPAL3™* VTAP Specifications.

5.4.3 Intervention assessments

Participants in the Intervention Group will be asked to return their weekly wear time journals each week by dropping off into a study mail box on the Track in the Minto Prevention and Rehabilitation

Centre at the UOHI. They will also exchange their VTAP for a newly charged device and be provided with a new wear time log.

5.4.3 Follow-up assessments

After 8 weeks of the study (end-of-intervention), participants will return to the UOHI for their last week of CR and all participants will once again be asked to wear an *activPAL3™* to monitor movement patterns. A research staff member who will be blinded to the participants' allocation will once again collect measures of aortic stiffness, blood pressure and resting heart rate and conduct a Modified Bruce Ramp Treadmill Test to estimate maximal aerobic power (VO₂max). Participants will be provided with a parking pass for aortic stiffness measurement visit.

Once again clinical measures (collected as part of standard of CR care) will be abstracted from the participant's chart (e.g. measured height (cm) and weight (kg) to compute BMI (kg/m²), waist circumference (cm), total cholesterol, high density lipoprotein (HDL), low density lipoprotein (LDL), triglycerides, and fasting HbA1c) and participant responses from the CR questionnaire will also be abstracted (e.g. self-reported exercise, HADS).

Participants in both groups will also be asked to complete a brief intervention satisfaction survey to assess satisfaction associated with wearing both the *activPAL3™* and VTAP monitors (see Evaluation Surveys).

Upon completion of the study, both groups will receive a fact sheet about sedentary behaviours including the hazards associated with sedentary time and 'Tips and Tricks' for reducing sedentary time (see Sedentary Fact Sheet).

5.5 Measures

The primary objective of this study is to assess the feasibility and usability of the *activPAL3™* and the VTAP in a CR setting to inform the development of a larger RCT. This will be assessed by examining:

- Recruitment rates;
- acceptability of intervention and wearing the *activPAL3™* and the VTAP using an evaluation survey (see Evaluation Surveys);
- completion and drop-out rates; and
- intervention adherence using wear time logs.

The primary outcome of the intervention focuses on changes in sedentary time measured by self-report and the *activPAL3™* over the 8-week intervention period. These outcomes will provide standard deviations to estimate an effect size for a future RCT. Secondary outcome measures will include:

- changes in MVPA (self-reported and objectively measured);
- changes in clinical outcomes (e.g., body weight, BMI, waist circumference, blood pressure, total cholesterol, HDL, LDL, triglycerides, and fasting plasma glucose);
- changes in measures of anxiety and depression (HADS);
- changes in self-efficacy to reduce sedentary time and increase PA;

- changes in HRQoL (SF-36);
- changes in aortic stiffness (PWV); and
- changes in maximal aerobic power (Modified Bruce Ramp Treadmill Test).

Measures and study time-line are provided in **Table 1**.

5.5.1 *Sedentary time*

The primary objective of this study is to evaluate the feasibility and usability of the *activPAL3™* in collecting time spent sitting, standing and lying in an on-site CR program. From this, the primary outcome of the RCT will be changes in sedentary time as measured both by self-report (sitting time from the International Physical Activity Questionnaire [see SIT-CR Baseline and Follow-up Questionnaires], sitting time from a FITS log [see SIT-CR Baseline and Follow-up Questionnaires], a sitting time question from the CR intake questionnaire), and objectively measured by the *activPAL3™* over 7-days. See the provided PAL Technologies Ltd. End User Licence Agreement.

5.5.2 *Moderate-to-vigorous intensity physical activity (MVPA)*

MVPA will be measured by both self-report (using the modified Godin Leisure-Time Exercise Questionnaire [15] [see the CR Questionnaire] and FITS log [see the SIT-CR Baseline and Follow-up Questionnaires]) and objectively measured using the *activPAL3™* over 7-days. Minutes of MVPA per week will be summed and used to assess goals and meeting guidelines. The device will also provide time spent in sedentary and light movement, as well as steps/day.

5.5.3 *Body composition*

Height (in cm), weight (in kg) and waist circumference (in cm) are measured as part of the regularly scheduled CR intake and final sessions by a nurse or physiotherapist using a standardized procedure. BMI will be computed from measured height and weight (kg/m^2). For the purpose of this study BMI will be analyzed both continuously and using adult categories of underweight ($<18.5 \text{ kg}/\text{m}^2$), normal weight ($18.50\text{--}24.99 \text{ kg}/\text{m}^2$), overweight ($25.0\text{--}29.99 \text{ kg}/\text{m}^2$) and obese ($\geq30.0 \text{ kg}/\text{m}^2$) [18]. Waist circumference will be analyzed both continuously and using adult cut-offs of $\geq 102 \text{ cm}$ (40 in.) for men and $\geq 88 \text{ cm}$ (35 in.) for women at increased risk of diabetes, heart disease and high blood pressure [19].

5.5.4 *Lipid profile*

Total cholesterol, HDL, LDL, and triglycerides will be extracted from the participant's CR file. These will be measured as part of CR evaluation practice at intake and upon completion.

5.5.5 *Fasting HbA1c*

Fasting HbA1c will also be extracted from the participant's CR file. This is also measured as part of CR evaluation practice at intake and upon completion.

5.5.6 *Aortic stiffness*

Aortic stiffness will be measured using the Mobil-O-Graph device (see Case Report Form). This device uses an algorithm based on blood pressure measurement taken at the upper arm to estimate the participants' aortic pulse wave velocity (PWV). The Mobil-O-Graph is a valid and reliable tool to measure PWV in clinical populations. Our lab has successfully used this device before in individuals with CVD. Participants are asked to sit at rest for five minutes prior to the measurement being obtained. A blood pressure cuff is placed on the individuals arm and four readings are taken. The test should take 5 to 10 minutes to complete. While measures are being taken the participant is asked to sit in a comfortable seated position, not to talk, to stay still and to keep their legs uncrossed. The Mobil-O-Graph will also supply resting heart rate and blood pressure values. These are both secondary outcome measures. Participants will be asked to follow the pretesting guidelines for PWV:

- No eating or drinking within 4 hours of the test
- No moderate or vigorous exercise within 12 hours of the test
- Void urine completely within 30 minutes of the test
- Abstain from alcohol consumption within 48 hours of the test
- Do not ingest diuretics, including caffeine before the assessment unless they are prescribed by a physician
- If you are in a stage of your menstrual cycle during which you perceive you are retaining water, postpone testing (female participants only)

5.5.7 *Blood pressure*

Resting blood pressure will be measured by the research coordinator or assistant using a. Blood pressure will be measured in a seated position after a five-minute rest period using a Mobil-O-Graph device (see aortic stiffness for further detail) that performs three measurements. An average of three measurements will be used for statistical analyses (see Case Report Form).

5.5.8 *Resting heart rate*

Resting heart rate will be measured by the research coordinator or assistant using a. Blood pressure will be measured in a seated position after a five-minute rest period using a Mobil-O-Graph device (see aortic stiffness for further detail) that performs three measurements. An average of the three measurements will be used for statistical analyses (see Case Report Form).

5.5.9 *Anxiety and depression*

Screening for anxiety and depression is carried out at baseline and follow-up CR visits using the Hospital Anxiety and Depression Scale (HADS) [16]. The HADS is a 14-item scale; seven of the items relate to anxiety and seven relate to depression. Each item on the questionnaire is scored from 0-3 with a final score between 0 and 21 for either anxiety or depression, with higher scores indicating greater anxiety and depression symptoms. See the CR intake questionnaire for the HADS.

5.5.10 *Self-efficacy*

Self-efficacy to reduce sedentary behaviour and increase light and moderate PA will be measured using a reliable questionnaire developed and validated by Adams [20]. The questionnaire includes twelve confidence scales (4 for each measure). Each item is a likert-type scale, ranging from 1 to 5.

Participants are asked to rate their level of confidence (not at all confident to completely confident) for specific sitting and PA behaviors. The average of the four items will produce the score for each particular sub-scale. See the SIT-CR Baseline and Follow-up Questionnaires for the self-efficacy questions.

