UOHI offers a supervised on-site 8-week CR program. The program consists of twice-weekly sessions (1 hour each) with a focus on aerobic and resistance exercise. There is currently no intervention component or outcome measure focusing on sedentary behaviours. This is unfavorable given the knowledge of the impact of sedentary behaviours on cardio-metabolic health. It is important to assess sedentary behaviours in this population to assess whether current programming affects sedentary behaviours or if more is needed to target these behaviours. This is important to note given that physical activity (PA)-focused interventions do not generally result in clinically meaningful reductions in sedentary behaviours [6]. Therefore, it is important to also investigate the feasibility of adding sedentary behaviour interventions to CR programming and whether these interventions can consequently further improve cardio-metabolic health. Using cues and prompting from wearable technology may provide a feasible way to reduce sedentary behaviours. A recent systematic review noted that interventions using education and prompts/cues were promising for reducing sedentary behaviours [7]. To date, most research using direct measures of PA and sedentary time have used research-grade accelerometers (e.g. ActiGraph®, Actical®, etc.). Research has shown that these monitors are not as valid for measuring sedentary time and postural changes as the *activPAL3™* monitor which is more precise and sensitive to changes in sedentary time [8].

The *activPAL3™* monitors have the capability to discern between standing and sitting which can increase our knowledge of movement patterns among CR participants. Additionally, the development of the *activPAL3™ VT* (VTAP) with vibrotactile feedback (VT), offers direct feedback to the wearer regarding time spent being sedentary. The prompts provided by these monitors have the capacity to reduce sedentary time and increase breaks from prolonged sitting by promoting individual awareness around movement patterns.

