2.0 PURPOSE

This research is timely given recent interest in the role of sedentary behaviours in both the primary and secondary prevention of cardiovascular disease. Sedentary behaviours have been shown to be high in patients with cardiovascular disease [5] and it is not yet known if current CR programming results in significant reductions of these behaviours, or whether a targeted component is warranted. It is also unclear if self-reported sedentary time measures can provide valid and reliable information for monitoring these behaviours in a CR setting, or whether more objective measures such as the *activPAL3™* are needed. This study has multiple purposes:

1. To inform the development of a larger randomize controlled trial;
2. to assess the feasibility and usability of the *activPAL3™* devices for measuring sedentary time in a CR setting and identify how it compares to self-report methods.
3. to describe changes in sedentary time that occur over standard CR with the use of prompting cues from the VTAP; and
4. to assess whether the addition of prompting cues can result in further decreases in sedentary behaviour and improvements in clinical outcomes, health-related quality of life (HRQoL), symptoms of anxiety and depression, self-efficacy, aortic stiffness, and aerobic capacity.

Results from this study will inform current gaps in the literature and help to generate recommendations for whether targeting sedentary behaviours in the CR setting is warranted.

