5.0 METHODS

5.1 Study design

This is a single-centre, two-armed randomized controlled trial (RCT) to evaluate the feasibility and usability of the *activPAL3™* in measuring sedentary time and the VTAP in providing sedentary prompts to reduce sedentary time in a CR setting (SIT-CR Study). The RCT (see **Figure 1** for study flow) will randomly allocate 32 individuals (16 males and 16 females) in a 1:1 ratio entering the CR program to either the Control Group (CR program) or to the Intervention Group (CR program + sedentary prompts from VTAP).

A week prior to their first class, participants will be asked to come to the UOHI to complete informed consent, a short questionnaire to assess employment patterns, self-efficacy to reduce sedentary behaviour and increase light and moderate PA, and HRQoL (see SIT-CR Study Baseline and Follow-up Questionnaires). Participants will also have their aortic stiffness, blood pressure and resting heart rate measured. In order to test for aortic stiffness participants will be asked to fast if possible, the study will provide a package of nuts and a glass of water at this first meeting. After the measurements, participants will then be asked to wear an *activPAL3™* during waking time for 7 days to collect baseline measures of sedentary time over one week prior to their first CR class.

On the day of their first CR class, participants will be asked to come in 30 minutes early to complete a Modified Bruce Ramp Treadmill Test to estimate maximal aerobic power. Once the test is complete, participants will be randomized in a 1:1 ratio (stratified by sex) to the Intervention or Control Groups. At this visit, participants in the Intervention Group will receive a wear time log sheet and a VTAP

monitor that will provide sedentary prompts to break up prolonged periods of sedentary time (prompts after 30 minutes of sedentary time). Participants in the Intervention Group receive a full-charged VTAP monitor each week when they attend their on-site CR class. Participants in the Control Group will continue with their regular CR class schedule.

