5.6.2 Analysis strategies

Baseline clinical and socio-demographic characteristics will be compared between groups to identify any chance differences that may have occurred despite random assignment. Outcome variables will be screened to determine whether they meet assumptions of normally distributed random variables with equal variances, and a descriptive examination will be performed, including plotting of relationships by condition. Retention rate will be computed by condition.

For the primary analyses, group differences in objectively measured and self-reported sedentary time (using the average of seven days) over the two time points (baseline and 8 weeks) will be examined using independent t-tests for parametric variables and Wilcoxon Mann Whitney test for nonparametric

variables. Similar analysis techniques will be used for secondary outcomes of interest (i.e., *activPAL*-measured and self-reported weekly MVPA; BMI, waist circumference, total cholesterol, HDL, LDL, triglycerides, fasting blood glucose, blood pressure, resting heart rate, aortic stiffness, HRQoL scores, self-efficacy scores, HADS scores, and maximum aerobic capacity).

Table 1. Study measurement timeline.

Visit	Screen	Baseline week	Cardiac rehabilitation							
			Week 1	Week 2	Week 3	Week 4	Week 5	Week 6	Week 7	Week 8/ follow-up
Length of time needed	30 min	1-2 hours	45 min	30 min	30 min	30 min	30 min	30 min	30 min	1-2 hours
Informed consent	C, I									
Diagnosis	C, I									
Age	C, I									
Sex (male/female)	C, I									
Height		C, I								
Weight		C, I								C, I
Waist circumference		C, I								C, I
Blood pressure (Mobil-O-Graph)		C, I								C, I
Resting heart rate (Mobil-O-Graph)		C, I								C, I
Blood work (cholesterol, HDL, LDL, triglycerides, HbA1c)		C, I								C, I
MVPA (CR questionnaire + activPAL3)		C, I								C, I
Questionnaires (self-efficacy, HRQoL, anxiety/depression)		C, I								C, I
Aortic stiffness (Mobil-O-Graph)		C, I								C, I
Aerobic power (Bruce Treadmill Test)			C, I							C, I
Sedentary time (activPAL3™, IPAQ, CR Questionnaire)		C, I								C, I
7-day activity journal (FITS)		C, I								C, I
Wear-time log			I	I	I	I	I	I	I	
Sedentary feedback (VTAP)			I	I	I	I	I	I	I	
Feedback survey										C, I

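### Self-reported sitting is a primary between-arm outcome although only the unblinded Intervention arm gets feedback on its sitting, so a self-report difference may mix changed sitting with changed reporting

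*Combined protocol and SAP*

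**What the plan says.** **Outcome.** Section 5.5.1 states that "the primary outcome of the RCT will be changes in sedentary time as measured both by self-report" and by activPAL3 over 7 days. The self-report sources are the IPAQ sitting item, the FITS log and a question in the CR intake questionnaire. Section 5.6.2 gives the primary analysis as "group differences in objectively measured and self-reported sedentary time (using the average of seven days" at baseline and 8 weeks), using independent t-tests or the Wilcoxon Mann Whitney test. Neither section ranks the device above self-report.

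**Intervention.** Section 5.4.2 says of the VTAP: "The monitor will provide participants with real-time feedback on their sedentary behaviour". It vibrates after 30 consecutive sedentary minutes and is worn "during waking hours for weeks 1 through 7". The Introduction expects such prompts to work "by promoting individual awareness around movement patterns".

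**Control.** Section 5.1: "Participants in the Control Group will continue with their regular CR class schedule". No sham or silent device is described. The follow-up part of 5.4.3 gives the sedentary fact sheet to both arms only on completion, and describes blinding only for the staff member who takes the aortic stiffness, blood pressure, heart rate and treadmill measures.

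**Validity of self-report.** Section 2.0: "It is also unclear if self-reported sedentary time measures can provide valid and reliable information" in CR. Section 4.2 makes validation of the log a secondary objective, and 5.4.1 links the baseline-week FITS log to that validation. No analysis of reporting error by arm is planned.

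**The concern.** The treatment is feedback on the same quantity that participants are then asked to report, and one arm alone receives it. Seven weeks of prompts could change how Intervention participants estimate or present their sitting, as well as how much they sit. A wish to show success would lower their reports and could create an apparent effect. Sharper awareness could raise their reports and hide a real effect. Randomisation balances reporting habits at entry; it does not balance a change in reporting that treatment produces afterwards.

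At stake is hypothesis 1 in 4.3, a superiority claim on sedentary time, and secondary objective 3 in 4.2. Section 5.5 also says that these outcomes will inform the effect size for a later trial, so a distorted self-report contrast could carry into that design. The device-versus-self-report comparison in 2.0 is exposed as well if week-8 data from prompted participants are pooled with the rest.

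**Working it through.** **1. The plan's own figure.** Inputs from 5.6.1: difference 91 min/day, SD 94 min/day, alpha 0.05 (sidedness not stated), power 80%, additions of 10% and 5%, total 32. For a two-sample t-test:
- One-sided 0.05 needs 14 per arm. 28 × 1.15 = 32.2, so 32 is reproduced.
- Two-sided 0.05 needs 18 per arm. 36 × 1.15 = 41.4, so 32 is not reproduced.

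The calculation covers a single sedentary-time comparison. Choosing activPAL3 for that comparison leaves N = 32 as it is.

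**2. Why the test cannot separate the two components.** Let T be the true between-arm difference in change in sitting, and B the between-arm difference in change of reporting error. If self-report tracks sitting one-for-one, the self-report contrast estimates T + B. The t-test and the rank test both act on that sum. Nothing in 5.6.2 identifies B.

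**3. Illustration of size.** Assumptions: T = 0; 14 analysable per arm (16 × 0.85 = 13.6, rounded up); two-sided 0.05. The documents give neither B nor an SD for self-report. I take B = 30 and 60 min/day, the ends of the MCID range in 5.6.1, purely as a scale. The plan's SD of 94 comes from a study of CR graduates whose listed title describes sedentary time as objectively measured. It is therefore a device-based figure, and I bracket it with 60 and 130.

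Standard error = SD × √(2/14). Noncentrality = B / standard error. Critical t on 26 df = 2.056. Rejection probability is from the noncentral t, counting both tails.

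| Assumed SD | Standard error | B = 30: noncentrality, rejection | B = 60: noncentrality, rejection |
|---|---|---|---|
| 60 | 22.7 | 1.32, 24.7% | 2.65, 72.1% |
| 94 | 35.5 | 0.84, 12.9% | 1.69, 37.0% |
| 130 | 49.1 | 0.61, 9.0% | 1.22, 21.7% |

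With B = 0 each entry would be 5%. With all 16 per arm and SD 94 the two figures are 14.1% and 41.6%.

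**4. The opposite direction.** With T = 91, SD 94 and 14 per arm, two-sided power is 69.4%. A reporting shift against the effect leaves 91 − 30 = 61 (power 38.0%) or 91 − 60 = 31 (power 13.4%).

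**5. Can the self-report-minus-device gap isolate B?** Not by itself. Suppose participants in both arms report 60% of true sitting (an assumption). A true reduction of 91 min/day then lowers self-report by 0.6 × 91 = 54.6 and the device value by 91. The gap differs between arms by 91 − 54.6 = 36.4 min/day with no difference in reporting behaviour. Adjusting for the baseline gap does not remove this.

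**The case against.** A reader might infer that reporting error is known to differ between the arms. The documents do not show that. The awareness sentence in the Introduction concerns movement, not recall, and the VTAP is described as signalling 30 unbroken minutes, not as telling wearers their daily total. Attention to sitting is not confined to one arm either: both answer self-efficacy items about reducing sedentary behaviour, and both wear activPAL3 and keep the FITS log in week 8. Prompts stop after week 7. All of this stands. It makes differential reporting a risk rather than a fact, but does not remove it, because knowledge of allocation and seven weeks of feedback remain.

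A second tempting reading is that the plan will validate the log on contaminated data. No section says so. Section 5.4.1 ties the baseline log to validation; what is missing is a statement of how week-8 data will be used.

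Third, activPAL3 is measured in both arms over the same windows, so a difference seen only in self-report would be visible, and this is a feasibility pilot. That limits the harm. It does not protect the self-report test, which would still be reported as a primary result.

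Finally, the percentages rest on an assumed shift and a borrowed SD. That also stands, so they show scale only.

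**Conclusion.** The concern holds as a risk of bias. Self-reported sitting should not by itself support a claim that the prompts work, because its between-arm contrast may mix behaviour with reporting and the planned tests cannot tell them apart. The facts behind this are in the documents, except that participants' lack of blinding is inferred from a vibrating device with no sham.

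Neither the sign nor the size of any reporting shift can be established from the documents. Under the stated assumptions (14 per arm, two-sided 0.05, no true effect, SD 130 down to 60), a 30 min/day shift gives about 9% to 25% rejections and a 60 min/day shift about 22% to 72%. These are not estimates of what will happen in this trial. A reader might also take a between-arm difference in the self-report-minus-device gap as proof of biased reporting; step 5 of the working shows why it would not be.

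The change is worth making because it is nearly free and the trial already collects the device measure in both arms.

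**What to change.** 1. In 5.5.1 and 5.6.2, base hypothesis 1 and secondary objective 3 on activPAL3 sedentary time. Report the IPAQ, FITS and CR questionnaire sitting measures as supportive outcomes that cannot on their own support a claim for the prompts. If the plan is also revised to name a lead sedentary-time measure, this is the same edit and should be made once.
2. In 5.6.2, add a descriptive analysis of self-report minus activPAL3 by arm and time point with 95% CIs. State that a between-arm difference in this gap can also arise from a true change in sitting when self-report does not track sitting one-for-one, and that the estimates will be imprecise at this size.
3. In line with 5.4.1, name the pre-randomisation baseline week as the main data for log validation and for the device-versus-self-report comparison. Show week-8 agreement by arm, not pooled.

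Cost: wording in two sections and one descriptive analysis of data already collected. There are no new visits, measures or participants, and N = 32 is unaffected. The downside is that self-report no longer counts as stand-alone efficacy evidence.
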